8.3.4 Removal of Subjects From Therapy or Assessments

In accordance with the Declaration of Helsinki, subjects may withdraw consent to continued participation in the study at any time without giving a reason. This right will be respected without affecting the routine treatment or care of the subject. If the reason for withdrawal is volunteered by the study subject it will be recorded in the subject's medical notes and in the electronic case report form (eCRF). The Principal Investigator (PI) will ensure the protection of the study subject's interests is prioritized.

Study subjects must discontinue study drug and be withdrawn from the study for any of the following reasons.

- Withdrawal of consent by the subject
- Withdrawal of assent and corroborated by parent(s)/legal guardian
- Any medical condition that the PI or sponsor determines may compromise the study subjects safety by continuing to receive study drug
- Pregnancy
- An AE or SAE which requires discontinuation from study drug
- Inability to remain under medical observation for the duration of the study
- Clinical risk of emergent suicidal ideation
- Noncompliance to:
 - Study schedule
 - Sleep and Symptom Daily Diary completion requirements
 - Major deviation from protocol mandated procedures
 - Concerns over subject study drug handling in terms of subject safety, abuse, and/or dependence potential as determined by the PI

- Any other situation where, in the opinion of the investigator or the sponsor, continuation of the study would not be in the interest of the subject
- Lack of efficacy
- Discontinuation of the study by the sponsor
- Regulatory authority decision or change in Independent Ethics Committee (IEC)/Institutional Review Board (IRB) opinion for drug safety problems

Irrespective of reason for withdrawal or discontinuation the PI must record the reason for withdrawal (if subject initiated withdrawal, this information must be voluntarily given by the subject). All data available for the study subject at the time of withdrawal/discontinuation must be recorded in the eCRF, unless specified otherwise by the subject. The PI will request that the subject return all study drug and may request a follow-up visit especially if any adverse event(s) remain unresolved.

In the event a subject does not return for a scheduled visit after withdrawal, every effort should be made to contact the subject. This should be documented. Every effort to document subject outcome should be made.

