PSG and MWT are at the discretion of the PI and consent of the subject. Early withdrawal study subjects will be followed for a week after the last dose of study drug. All SAEs and nonserious AEs assessed by the PI as related to the study drug should be followed to resolution or until the PI assesses them to be chronic or stable.

It will be left to the investigator's clinical judgement whether or not an AE is of nature, or severity to require the subject's removal from treatment. A subject may also voluntarily withdraw from treatment due to what is perceived as an intolerable AE. If either of these occurs, the subjects must undergo an end-of-study assessment and receive appropriate care under medical supervision until symptoms cease or the condition becomes stable.

Withdrawal due to an AE should be distinguished from withdrawal due to lack of efficacy.

If the subject withdraws due to a SAE, the SAE must be reported in accordance with SAE reporting requirements.

Randomized subjects who have received at least 1 dose of study drug, who withdraw from the study prematurely will not be replaced.

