Visit 4 includes a full efficacy assessment (evaluation of the 6.0 g efficacy). Procedures at this visit include:

- Compliance with drug washout requirements
- Confirmation of continued eligibility
- Assess study restrictions compliance: (i) abstinence from alcohol, (ii) smoking restrictions, and (iii) all other study restrictions
- Assess for drug abuse and dependence. Clinical judgement to be exercised in determining need for performing urine drug screen for benzodiazepines, cannabis, cocaine, opiates, and barbiturates
- Assess compliance with drug handling, management, and safety requirements
 - Confirm subject is adhering to requirement to eat at least 2 hours before taking study drug
 - Subject re-education on study drug safety and handling and study-related procedures if deemed necessary by PI
- Review and record of concomitant medication
 - Assess for adherence to prohibited medication requirements.
- Document any AEs
- Collect CGI assessment of improvement in sleepiness (investigator blinded to MWT results)
- Administer "since last visit" C-SSRS questionnaire
- Perform physical examination if determined clinically indicated by the PI
- Record vital signs (systolic and diastolic BP and heart rate)
- Perform urine pregnancy test (female subjects)
- Review and confirmation of ePRO diary and questionnaire completion (on subject questioning and ePRO check).
 - Self-recorded study drug compliance record (with returns check)

- Compliance with Sleep and Symptom Daily Diary completion requirements for the past 3-week period. Completion of ESS (subject questionnaire)
- Overnight PSG
 - Next-day 5 hour nap MWT
- Dispense drug and perform accountability
- ePRO device handling and ePRO completion requirements and consequences of poor compliance will be discussed again with the study subject
 - Study subjects will be instructed to complete their Sleep and Symptom Daily Diary on a daily basis for the next 2 weeks

If the PI is concerned that the study subject will be unable to comply with FT218 study drug and study requirements following training and education session the subject will be informed and withdrawn from study.

- Schedule Visit 5 with the study subject
- Update IRT system with subject's details for next visit and study drug returns

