9.2.5 Period 3c(ii): Visit 7 (Week 11, Day 1) Stabilization

Stable dosing:

- Week 11: 1st week on study drug in this period: 9.0 g/night of FT218 or placebo
- Week 12: 2nd week on study drug: 9.0 g/night of FT218 or placebo
- Week 13: 3rd week on study drug: 9.0 g/night of FT218 or placebo

Visit 7 includes a partial efficacy assessment. Procedures at this study visit include:

- Compliance with drug washout requirements
- Confirmation of continued eligibility
- Assess study restrictions compliance: (i) abstinence from alcohol, (ii) smoking restrictions, and (iii) all other study restrictions
- Assess drug abuse and dependence. Clinical judgement to be exercised in determining need for performing urine drug screen for benzodiazepines, cannabis, cocaine, opiates and barbiturates
- Assess compliance with drug handling, management, and safety requirements
 - Confirm subject is adhering to requirement to eat at least 2 hours before taking study drug

- Subject re-education on study drug safety and handling and study-related procedures if deemed necessary by site PI
- Review and record of concomitant medication
 - Assess for adherence to prohibited medication requirements.
- Document any AEs
- Collect CGI assessment of improvement in sleepiness (investigator blinded to MWT results)
- Administer “since last visit” C-SSRS questionnaire
- Perform physical examination if determined clinically indicated by the PI
- Collect vital signs (systolic and diastolic BP and heart rate)
- Perform urine pregnancy test (female subjects)
- Review and confirmation of ePRO diary and questionnaire completion: (on subject questioning and ePRO check)
 - Self-recorded study drug compliance record (with returns check)
 - Compliance with Sleep and Symptom Daily Diary completion requirements for the past 2-week period. Completion of ESS (subject questionnaire)
- Dispense drug and perform accountability
- ePRO device handling and ePRO completion requirements and consequences of poor compliance will be discussed again with the study subject
 - Study subjects will be instructed to complete their Sleep and Symptom Daily Diary on a daily basis for the next 3 weeks.

If the PI is concerned that the study subject will be unable to comply with FT218 study drug and study requirements following training and education session the subject will be informed and withdrawn from study.

- Schedule Visit 8 with the study subject

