9.2.6 Period 3c(iii) Visit 8 (Week 13, Day 7) End of Study (EOS)

This visit includes a full efficacy assessment (evaluation of the 9.0 g efficacy).

- Compliance with drug washout requirements
- Confirmation of continued eligibility
- Assess study restrictions compliance: (i) abstinence from alcohol, (ii) smoking restrictions, and (iii) all other study restrictions
- Assess drug abuse and dependence. Clinical judgement to be exercised in determining need for performing urine drug screen for benzodiazepines, cannabis, cocaine, opiates and barbiturates
- Assess compliance with drug handling, management and safety requirements
 - Confirm subject is adhering to requirement to eat at least 2 hours before taking study drug
- Review and record of concomitant medication
 - Assess for adherence to prohibited medication requirements
- Document any AEs

- Complete CGI assessment of improvement in sleepiness (investigator blinded to MWT results)
- Administer “since last visit” C-SSRS questionnaire
- Perform full physical examination
- Collect weight
- Collect vital signs (systolic and diastolic BP and heart rate)
- Collect samples for hematology, biochemistry, and perform urine pregnancy test (female subjects)
- Collect sample for urinalysis
- Perform 12-lead ECG after subject is supine for 5 minutes
- Review and confirmation of ePRO diary and questionnaire completion: (on subject questioning and ePRO check)
 - Self-recorded study drug compliance record (with returns check)
 - Compliance with Sleep and Symptom Daily Diary completion requirements for the past 3-week period. Completion of ESS (subject questionnaire)
- Overnight PSG
 - Next-day 5 hour nap MWT
- Perform drug accountability and reconciliation
- Update IRT system with EOS details and final subject drug accountability
- Obtain ePRO device from subject and place in on-site safe storage
- Schedule follow-up visit with study subject

9.3 Follow-up Period – Period 4

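### Diary noncompliance is a mandatory reason to stop drug and leave the study, which can cost 9 g MWT and CGI data that do not depend on the diary

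*Protocol*

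**What the plan says.** Protocol 8.3.4 opens its list with "Study subjects must discontinue study drug and be withdrawn from the study for any of the following reasons". One entry, under noncompliance, is "Sleep and Symptom Daily Diary completion requirements". It is not limited to NT1, and no number of missed entries is attached to it.

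The same section says of early withdrawals that "PSG and MWT are at the discretion of the PI and consent of the subject", and that dosed subjects "who withdraw from the study prematurely will not be replaced". Protocol 9.4 adds that when an unscheduled visit leads to withdrawal, the end-of-study procedures are performed.

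Section 9.2 puts steps before withdrawal. At Visits 4 to 7, "ePRO device handling and ePRO completion requirements and consequences of poor compliance will be discussed again with the study subject". Visits 3 to 7 also carry a sentence beginning "If the PI is concerned that the study subject will be unable to comply with FT218 study drug and study requirements"; if that concern remains after training, the subject is told and withdrawn.

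On the analysis side, Protocol 11.9.1 makes MWT and CGI the co-primary endpoints for daytime sleepiness in both narcolepsy types. The only diary-based primary endpoint is the number of cataplexy attacks (NCA), analysed in NT1 only. Fewer than 3 diary days in a week makes the value missing (Protocol 11.3.1 and 11.9.1; SAP 2.6.1.2).

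**The concern.** The rule ties continued treatment and follow-up to one instrument. MWT and CGI at 9 g are the first step of the testing order in Protocol 11.9.1.2. If either fails, neither symptom can be claimed at 9 g and the lower doses are not tested. A subject who attends visits and takes the drug can still be removed from both of those tests because of the diary. For an NT2 subject, the diary supplies no primary endpoint at all.

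The exit also gains nothing for the diary. A sparse week is already handled as missing, and withdrawing the subject ends later diary collection together with MWT and CGI.

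The wording is firmer here than for dosing. Protocol 8.4.6 says that a subject who does not comply with dosing *may* be withdrawn, and more than 2 missed doses in a period leads to an assessment for potential withdrawal.

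**Working it through.** **Step 1: what is lost, by time of withdrawal.** MWT is measured at the full assessments only: Visit 4 (6 g), Visit 6 (7.5 g) and Visit 8 (9 g). Visits 5 and 7 exclude it (SAP 4.1.2). CGI is rated at Visits 4 to 8, so the 9 g ratings are those at Visits 7 and 8. Diary review is tied to visits: at Visit 7 it is "Compliance with Sleep and Symptom Daily Diary completion requirements for the past 2-week period", and at Visit 8 "Compliance with Sleep and Symptom Daily Diary completion requirements for the past 3-week period".

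| Withdrawn at | Diary weeks just reviewed | Scheduled 9 g data kept | Scheduled 9 g data lost |
|---|---|---|---|
| Visit 4, 5 or 6 | 1–3, 4–5 or 6–8 | none | CGI at Visits 7 and 8; MWT at Visit 8 |
| Visit 7 | 9–10 | CGI at Visit 7 | CGI and MWT at Visit 8 |
| Visit 8 | 11–13 | all | none |

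An MWT done at withdrawal reflects the dose at that time. It can be a 9 g value only from Week 9.

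**Step 2: how many subjects.** The documents give no diary completion rate and no visible on-treatment threshold. Sample size, effect size, standard deviation and dropout rate are not in the public text, so there is no plan figure to reproduce. What follows only gives a sense of scale; every input is an assumption.

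Assume that the screening threshold (at least 4 entries per week, Protocol 8.3.2) also applies on treatment. With daily completion p and independent days, the chance of a short week is P(Binomial(7, p) ≤ 3):

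- p = 0.95: 0.000194
- p = 0.90: 0.002728

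At least one short week in Weeks 1–10, the weeks reviewed by Visit 7, has probability 1 − (1 − s)^10, where s is the weekly chance:

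- p = 0.95: 1 − (1 − 0.000194)^10 = 0.19%
- p = 0.90: 1 − (1 − 0.002728)^10 = 2.69%

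If completion varies between subjects (beta-distributed, intraclass correlation 0.05 to 0.10, given no short week in the 3 screening weeks), these become 1.9–3.2% and 7.1–8.6%. Two or more short weeks, closer to persistent noncompliance, then occur in 0.2–0.8% and 1.4–2.6%.

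**Step 3: what such losses would do.** Suppose a test has assumed design power P and loses a fraction w of its 9 g observations, with no credit for earlier repeated measures. Its power becomes Φ((1.96 + z_P)·√(1 − w) − 1.96), with 1.96 + z_P = 3.2415 for 90% and 2.8016 for 80%.

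| w | from 90% | from 80% |
|---|---|---|
| 0.2% | 89.9% | 79.9% |
| 2.7% | 89.2% | 78.9% |
| 8.6% | 87.3% | 76.4% |

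These w values treat every subject with one short week as withdrawn, which the protocol does not say. They are upper figures under each completion assumption, they are not specific to NT2, and they are not estimates for this trial.

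**The case against.** The strongest reply is that the mandatory wording bites only once the completion requirements are breached, and the breach point cannot be seen. Protocol 10.1.1.3, the diary section, shows no text, which may be redaction. If that text defines noncompliance as sustained, the rule reaches very few people. Counselling and an investigator-judged step also come first. This stands, and it limits the point in three ways:

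- A reader might infer that one missed entry or one poor week forces withdrawal. The documents do not support that.
- A reader might infer a measurable power loss. With completion, threshold, design power and withdrawal rate all assumed, none can be claimed.
- A reader might infer that the sections contradict each other. They do not. Section 9.2 describes steps on the way to the outcome that 8.3.4 requires, and the contrast with 8.4.6 is one of firmness.

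The diary is also not idle in NT2. It is a listed efficacy assessment, the secondary and exploratory endpoints are redacted, and under Protocol 10.1.2.1 it records symptoms that are not reported as adverse events. The ePRO device also carries the drug adherence record, so a subject who stops using it may be a real concern with a Schedule I drug taken at home. That justifies keeping discretion to withdraw. It does not justify compulsory exit for diary lapses alone.

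Finally, simply changing *must* to *may* would leave about 60 centres to their own judgement, and recording lapses as deviations could remove retained subjects from the per-protocol set. Both objections are sound, and they shape the fix.

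**Conclusion.** The point holds as an optional improvement. As written, 8.3.4 requires a subject found noncompliant with the diary to give up both drug and study, whatever the narcolepsy type. That can forfeit the single scheduled 9 g MWT and one or both 9 g CGI ratings, and it returns no diary information. This conclusion rests on the wording and the visit schedule, not on any assumed rate.

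The size is unknown and probably small. It depends on an on-treatment threshold that is not visible and on how sites apply the investigator's judgement. Confidence is medium for that reason.

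**What to change.** - **Protocol 8.3.4:** take diary completion off the mandatory list. State that diary lapses alone lead to retraining and are not by themselves a reason to stop drug or leave the study, so the subject continues to the scheduled CGI and MWT visits. Keep withdrawal available where the investigator and sponsor have a safety, drug-handling or diversion concern.
- **Protocol 9.2:** apply the same rule to the investigator-concern sentence at Visits 3 to 7.
- **Analysis:** keep the existing rule of fewer than 3 days as missing for NCA.
- **Per-protocol set (Protocol 11.3.2 and 11.13; SAP 3.2):** state that diary lapses alone do not exclude a subject from the per-protocol analysis of MWT and CGI. The current text excludes for deviations from visits and procedures, with no visible distinction between major and minor.

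The cost is wording plus the usual ethics approval of an amendment and, because the SAP was prepared for a Special Protocol Assessment, alignment with that submission. Training needs are already assessed at every visit (Protocol 8.4.9). The real downside is that a few subjects stay in with sparse diaries. That thins NCA in NT1, any diary-based exploratory endpoints, and the capture of symptoms not reported as adverse events.

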8.3.4.1 Pregnancy

Study subjects may not be pregnant or nursing during the course of this study as indicated in the inclusion and exclusion criteria. Subjects of childbearing potential include all females who are not postmenopausal for at least 1 year before the screening visit and are not surgically sterile.

All female subjects of childbearing potential must agree to practice 2 effective methods of contraception, from the time of the signing of informed consent through the last dose of study drug or agree to completely abstain from heterosexual intercourse.

For all women of childbearing potential a serum pregnancy test will be performed at screening and a urine pregnancy test will be performed at least 7 days before commencing FT218/placebo dosing. The results must be available, documented and negative before the first dose of study drug is administered.

After study drug is dispensed at Visit 3, urine pregnancy tests will be repeated at each study visit throughout the remainder of the study, including the final study visit (Visit 9) or at the withdrawal visit if the subject withdraws from the study.

The investigator must report to the sponsor any pregnancy occurring in a study subject, during the subject's participation in this study. The study Pregnancy Reporting Form will be used. The report will be submitted within the same timelines as an SAE.

For a study subject, the outcome of the pregnancy should be followed up carefully, and any abnormal outcome of the mother or the child should be reported. In some circumstances, it may be necessary to monitor the development of the newborn for an appropriate period after delivery.

Although pregnancy is not an SAE, and an elective abortion is not an SAE, any spontaneous abortion and/or any pregnancy that meets any regulatory serious criterion, or any pregnancy with an outcome for the pregnant person or the infant that meets regulatory serious criterion will be captured as an SAE.

8.4 Investigational Product

The active ingredient of FT218, sodium oxybate (GHB), is a CNS depressant. Drug product formulations containing GHB that have no marketing authorization are classified as Schedule I controlled substances within the US. For all non-US sites classification across regions can vary, local/regional classification will apply.

This study has been developed to ensure all local legal and regulatory requirements for the safe handling of Schedule I/Controlled Drug for all participating regions in the CLFT218-1501 clinical study are adhered to.

8.4.1 Investigational Products Administered

8.4.1.1 Definition of a Schedule I/Controlled Drug Substance

A substance where there is no current accepted medical use in treatment, a lack of accepted safety for therapeutic use under medical supervision and a high potential for abuse.

8.4.1.2 FT218 Study Drug Risk Management

The CLFT218-1501 operational framework will be structured to mitigate safety, abuse, misuse, and diversion risks associated with FT218. The framework will:

1. Safeguard subject safety and mitigate abuse, misuse, and diversion risks, and minimize potential for public-health risk through the implementation of best practice handling and distribution processes and procedures

2. Allow for robust evaluation of emerging safety data and FT218 study drug management for detection of risk in terms of subject safety, abuse, and misuse potential

8.4.1.3 Specification for Managing Controlled Substances

Systems and structures will be put in place to ensure compliance in the handling, distribution, prescription, and management of FT218. This will include:

1. A “closed system” of FT218 distribution
2. All study investigators and investigative site facilities will be assessed and qualified in advance of site set up. Only investigative sites meeting requirements will be qualified for participation in this clinical study. All qualified investigative sites will be monitored on an ongoing basis for the duration of the clinical study to ensure ongoing compliance with all legal and regulatory requirements as applicable to the FT218-1501 clinical study
3. Subject education on FT218 handling
4. Key investigator requirements include but are not limited to:
 - a. Authorization to prescribe the FT218 controlled substance by the jurisdiction in which they are licensed to practice
 - b. Evidence of current registration (Drug Enforcement Agency in the US, as per local/regional requirements for non-US sites) for the handling of the FT218 controlled substance
 - c. Complying with all FT218-1501 clinical study requirements and all legal and regulatory requirements specific to the safe handling and management of the FT218 drug product
 - d. Awareness of ramifications of noncompliance with requirements

All site specific approvals, registration forms and/or exemptions (if applicable for the latter) will be filed in the local study file at each site and a copy from each site will be provided for filing in the Trial Master File.

